8.11 Randomization

Subjects who are eligible to participate in the study will be randomized to one treatment group at the time of completion of screening.

8.12 Assessment of Offloading

The following questions will be asked to assess the performance of the offloading during the Screening and Treatment Phase visits and at selected follow-up visits:

- Did the subject have the offloading device with him or her or is the TCC cast still present? (Yes/No)
- What percentage of the time is the subject using the offloading device while not sleeping?
 (Note: heel ulcers might still need to be offloaded while sleeping.)

8.13 Semmes Weinstein Monofilament Test for Peripheral Neuropathy

This is a non-invasive topical evaluation of neuropathy with a monofilament wire and with vibratory evaluation. The test will be performed in a standard manner with 10 points being evaluated on each visit. At each point, the Investigator asks the subject whether they can feel the filament and / or vibration (yes or no). Note: If a subject is missing a body part called out in the Semmes Weinstein test and with vibratory, the most skin in the area where the missing body part is located is used for the test.

8.14 SnapshotNIR

SnapshotNIR imaging for tissue perfusion will be obtained at SV1, TV1 pre-randomization, TV2, TV4, TV7, and EOS1. The procedure is described in Appendix H.

Confidential Page 48 of 73

9 Data and Statistical Analyses

9.1 Data Analysis

This study consists of primary, secondary and exploratory/tertiary (research) endpoints. Data analysis of study endpoints includes use of validated DFU wound healing measures, quantitative and qualitative analyses, as well as exploratory methodologies. Table 4 below details each study endpoint, corresponding data, and planned analyses.

TABLE 4: ETS WOUND CARE, LLC DFU ENDPOINT DATA ANALYSIS

Endpoint	Endpoint Description	Supporting Study Data	Endpoint Analysis
Primary	Comparison of the proportion of index ulcers "healed" at 12 weeks	Investigator assessment of healing (100% epithelization w/no drainage), measurements of ulcer size using digital imaging and photos	Adjudication panel will determine using photographs of the DFU
	Proportion of Index Ulcers healed at 6 weeks		
	PAR at 6 and 12 weeks	Digital imaging	Mathematical wound area change
	Time to healing within 6 and 12 weeks	Primary endpoint	Mathematical time based on healing
Secondary	Changes in peripheral neuropathy	Semmes Weinstein with vibratory	Mathematical change in scores
	Changes in wound quality of life	WOUND-Q (Quality of life tool)	Mathematical change in scores
	Change in pain levels during trial	NPRS	Mathematical change in scores
	Difference in cellulitis and/or infection at 12 weeks	Observation	Count of positive and negative responses
Exploratory/Tertiary	Changes in tissue perfusion of wound bed and periphery with treatment	SnapshotNIR	Exploratory

9.2 Statistical Analysis

Descriptive statistical methods will be used to summarize the data from this study with hypothesis testing performed for the primary and other selected efficacy endpoints. All testing for endpoints will be two-sided with alpha set at .05 level of significance if no statistical testing is done at the interim analysis at 0.044 if statistical testing is done at N=240.

A formal Statistical Analysis Plan (SAP) will be created prior to database lock. The primary endpoint analysis will be at 12 weeks and a series of secondary and exploratory/tertiary

Confidential Page 49 of 73

endpoints will be analyzed at 6 and 12 weeks. The SAP will provide a more technical and detailed description of the proposed data analysis methods and procedures. Any deviation from the analyses outlined in the protocol will be described in the most current version of the SAP. All statistical analyses will be conducted using PASW 28.

The primary study hypothesis is that the proportion of wounds healed at 12 weeks, after up to 12 weeks of SOC with MIRRAGEN™ and SOC with FIBRACOL™, will be equal for Groups 1 and 2. Formally, H0: I1–I2 = 0; HA: I1–I2 = D1≠0, where I1 is the proportion of wounds healed in Group 1, I2 is same metric for Group 2, D1 is the difference (I1–I2); assuming the alternative hypothesis and statistical test used is chi square/Fisher exact test. Analysis may be adjusted using generalized linear modeling based on available variables at baseline known to affect wound healing.

Group sequential trials with sample sizes of 120 and 120 at the final look achieve 100% power to detect a difference of 0.35 between group 1 (the MIRRAGEN™ group) (proportion 0.70) the control group (SOC with FIBRACOL™) proportion of 0.35 at the 0.049 significance level (alpha) using a two-sided Z-Test (Pooled).

The populations defined for analysis will include the intent-to-treat (ITT) and per protocol (PP). Additional analysis populations may be defined to evaluate study results. Any additional analysis populations will be defined in the SAP.

Envelopes will be created with a random allocation sequence, which will be composed of a random sequence of block sizes of 10 designed to achieve a balanced design.

One interim analysis will be performed (N~100). The object of the interim analysis is to assess subject outcomes between the groups, in particular to assess any adverse effects or events, such as infection and to recalculate sample size for the primary endpoint.

Primary analysis: Proportion of index wounds closed at 12 weeks (group 1 versus group 2) using chi square. Analysis will be adjusted using logistic regression.

Secondary analysis: (1) proportion of Index Wounds closed at 6 weeks (group 1 versus group 2) using chi square; (2) time to heal within 6 and 12 weeks using Kaplan-Meier analysis; (3) PAR at 6 and 12 weeks (group 1 versus group 2) using the Mann-Whitney test; (4) mean difference between groups 1 and 2 of change in weekly peripheral neuropathy score surrounding the DFU using the Semmes Weinstein monofilament with vibratory procedure based on GLM repeated measures; (5) mean difference between groups 1 and 2 of change in WOUND-Q score based on difference between baseline and 12 weeks using t test if data are normal or Kolmogorov–Smirnov test if data are non-normal; and (6) mean difference between groups 1 and 2 of change in weekly wound pain VAS score based on GLM repeated measures.

Control of the familywise error rate (all endpoints) will be achieved through the Hochberg stepup procedure.

Every effort will be made to obtain required data at each scheduled evaluation from all subjects who have been randomized and treated. Subjects who are withdrawn or lost to follow-up will be included in the ITT analysis of primary and secondary endpoints using data imputation methods detailed in the SAP. Sensitivity analysis will also be conducted for the primary endpoint using different imputation algorithms.

10 Adverse Effects and Events (Definitions and Reporting)

The Investigator is responsible for the detection and documentation of any events meeting the criteria and definition of an adverse effect or adverse event (AE), as described in this protocol.

Confidential Page 50 of 73

During the study when there is a safety evaluation, the Investigator or site staff will be responsible for detecting, documenting, and reporting any adverse effect or adverse event, as detailed in this Section of the protocol.

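### Section 9.2 gives two incompatible levels, 0.044 and 0.049, for the group-sequential design at N=240, and states no interim level that would reconcile them

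*Combined protocol and SAP*

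**What the plan says.** All of the relevant text is in Section 9.2 (Statistical Analysis) of the protocol.

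- **Testing clause.** All endpoint tests are two-sided, at "05 level of significance if no statistical testing is done at the interim analysis at 0.044 if statistical testing is done at N=240". The quote omits the decimal point before 05, and a conjunction seems to be missing in the middle. I read it as 0.05 if nothing is tested at the interim, and 0.044 at N=240 if something is.
- **Power statement.** "Group sequential trials with sample sizes of 120 and 120 at the final look achieve 100% power" for 0.70 against 0.35, "at the 0.049 significance level (alpha) using a two-sided Z-Test (Pooled").
- **Interim.** "One interim analysis will be performed (N~100"). Its purpose: "The object of the interim analysis is to assess subject outcomes between the groups". The emphasis is on safety, and the number of subjects needed for the primary comparison is to be worked out again. No interim significance level, spending function or stopping boundary is given, here or elsewhere in the supplied document. Nor is it said whether efficacy will be tested at that look.
- **Multiplicity.** The Hochberg step-up procedure is to control familywise error over all endpoints.
- **Deferral.** "A formal Statistical Analysis Plan (SAP) will be created prior to database lock". On its content, the section adds: "The SAP will provide a more technical and detailed description of the proposed data analysis methods and procedures".

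**The concern.** The testing clause and the power statement describe the same final look of a two-look design and give different levels. In such a design the final level follows from the overall alpha, the interim level and the timing of the interim. The plan gives only an approximate timing and no interim level. A reader therefore cannot tell which final level is right, or what overall type I error the design holds.

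At stake is the threshold for the final tests. It carries into every Hochberg step, because each step is a fraction of that level. The timing of the SAP adds to this: the interim looks at outcomes between groups in an open-label trial, while the SAP is required only by database lock. Nothing in the plan obliges anyone to settle the levels, or whether interim efficacy testing takes place, before those outcomes are seen.

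**Working it through.** **Inputs.** From Section 9.2: 120 per arm, 0.70 against 0.35, levels 0.05, 0.044 and 0.049 (all two-sided), one interim at N~100. Assumption: the interim falls at exactly 100 of 240, so the information fraction is t = 100/240 = 0.417.

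**1. The plan's own power figure.** For the pooled Z-test, power = Φ[(0.35 − z·SE0)/SE1]. SE0 = √(2 × 0.525 × 0.475/120) = 0.0645 and SE1 = √((0.70 × 0.30 + 0.35 × 0.65)/120) = 0.0604. At 0.049, z = 1.969 and the bracket is 3.695, which gives 99.989%. At 0.05 it is 99.989% and at 0.044 it is 99.987%. The stated 100% reproduces by rounding, and power does not help to choose between the levels.

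**2. Interim level implied by each final level.** Overall error = 1 − P(|Z1| < c1, |Z2| < c2), with Z1 and Z2 bivariate normal and correlation √0.417 = 0.645. Solving for the interim level:

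| Overall alpha | Final level | Interim level needed |
|---|---|---|
| 0.05 | 0.049 | 0.0024 |
| 0.05 | 0.044 | 0.0104 |
| 0.049 | 0.044 | 0.0089 |

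The last row covers the reading that 0.049 is the overall alpha of the design. The two figures can then coexist, but the overall alpha differs from the 0.05 of the no-testing branch. None of the three interim levels is in the plan.

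**3. Crossing the sentences.** Interim 0.0104 with final 0.049 gives 5.5% overall. Interim 0.0024 with final 0.044 gives 4.5%.

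**4. Where the figures could come from.** O'Brien-Fleming-type spending at t = 0.417 spends 2 − 2Φ(1.960/0.645) = 2 − 2Φ(3.036) = 0.0024 at the interim and leaves a final level of 0.0490, which matches the power statement. Pocock-type spending leaves 0.030. Classical two-look O'Brien-Fleming at t = 0.5 gives 0.048. None of these standard boundaries gives 0.044.

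**5. Effect on the primary decision.** Hochberg was simulated with an assumed family of seven (the primary plus the six numbered secondary analyses), at level 0.044 and at 0.049. The table shows how often the primary decision differed.

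| Setting | Decision differs |
|---|---|
| Global null | 0.07 to 0.13% |
| All seven with mean Z = 2 | 1.5 to 1.6% |
| All seven with mean Z = 2.6, independent | 2.1% |
| Primary mean Z = 2.4, others 3.0, independent | 2.2% |
| Primary near the planned effect, others null | about 0.035% |

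Most changes occur with the primary p-value outside 0.044 to 0.049. For example, with a primary p of 0.0066 and all others at 0.5, the primary is rejected at 0.049/7 = 0.0070 but not at 0.044/7 = 0.0063.

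**The case against.** The best defence is that the testing clause is the decision rule and 0.049 is only a planning input. Power is the same at either level, so no sample-size conclusion changes. This stands as far as power goes. But a reader who takes 0.044 as the rule still lacks the interim level of about 0.0104 that would make it hold 0.05, and the power statement still describes a different design.

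A second defence is that the SAP will supply the detail. Deferral is legitimate for matters left open. Two figures already printed that disagree are not left open, and the SAP deadline does not protect against settling them after the interim.

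Third, Hochberg need not name its own alpha, because the testing clause covers all endpoint tests. That is right: it is not a separate omission. It inherits the same ambiguity.

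Some stronger readings are tempting, and the documents do not support them:

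- *Three conflicting levels.* The 0.05 and 0.044 are conditional alternatives and do not conflict.
- *Type I error of 8% or more.* An interim test at an unadjusted 0.05 would give 8.1% (final 0.044) or 8.5% (final 0.049), but nothing in the plan proposes such a test.
- *Inflation from re-sizing.* Error of about 5.1 to 6.1% would follow if the observed arm difference drove N and the final test were at 0.05. The text neither states nor excludes such a rule, so the figure is hypothetical.
- *The effect is limited to primary p-values between 0.044 and 0.049.* The probability of that band is not an upper bound, because alpha also moves every lower Hochberg step.

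**Conclusion.** The inconsistency is real and should be corrected. As written, the final level after interim testing is 0.044 or 0.049 depending on the sentence followed, and no stated interim level completes either design. If the sentences are crossed, overall error is 4.5% or 5.5% instead of 5%. The primary decision would rarely change: about 0.1% of trials under the global null and up to about 2.2% in the settings tried. Power is unaffected.

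These figures rest on an interim at 100 of 240, normal theory for the two looks, and an assumed family of seven endpoints with illustrative effects and correlations. The conflict itself rests on none of them; it is visible in the text. The reason to act is that a decision threshold should have one value, fixed before comparative data are seen.

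**What to change.** In Section 9.2:

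1. State an overall two-sided alpha of 0.05 and one interim/final pair from a named spending function. O'Brien-Fleming-type spending gives 0.0024/0.049 at 100 of 240 and agrees with the existing power statement; replace 0.044 accordingly.
2. If 0.044 is to stay as the final level, state interim 0.0104 and change the power statement to match.
3. Recompute the final level from the named function if the interim or final N differs. O'Brien-Fleming-type spending gives 0.0014/0.0494 with the interim at 90 of 240 and 0.0038/0.0485 at 110.
4. State that Hochberg at the final analysis uses that same final level.
5. Fix these levels, and whether efficacy will be tested at the interim, before any interim data are opened, not merely before database lock.

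The cost is a wording change. The final test becomes slightly stricter than 0.05, with power still about 99.99% at the planned effect. How the sample size is recalculated, and whether blinded to arm, is a separate recommendation and not part of this inconsistency.

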3.00Pe	Group 2: SOC primary dressing with FIBRACOL™
Study Design	Multi-center, open label, randomized controlled trial
Sample Size	For this RCT, N = up to 240 subjects
Centers	Up to 15 centers within the United States, Open/competitive enrollment.
Endpoints	Primary endpoint: - The proportion of subjects that obtain complete closure over the 12-week treatment period Secondary endpoints: - The time to achieve complete wound closure of the target ulcer by the end of 12 weeks
	 Percentage wound area reduction from TV1 to TV13 measured weekly with digital photographic planimetry and physical examination
	The number and type of Treatment Emergent Adverse and Serious Adverse Events
	 Change in peripheral neuropathy of the target foot assessed using the standard 10-point Semmes-Weinstein monofilament exam [Time Frame: TV1, TV3, TV7, TV9, and EOS1]
	 Change in pain in the target ulcer assessed using the NPRS scale. [Time Frame: TV1, TV3, TV7, TV9, and EOS1]

Confidential Page 10 of 73

Version 2.0 Date: May 12, 2023 Change in quality of life using WOUND-Q assessment [Time Frame: SV1, TV3, TV7, EOS1] **Exploratory Endpoint:** Difference in cellulitis and/or infection at 12 weeks Use of near-infrared tissue oxygenation imaging assessment of wounds at select sites to evaluate changes in vascularization/oxygenation of wounds with treatment (Kent Imaging SnapshotNIR: Time Frame: SV1, TV1 pre-randomization, TV2, TV4, TV7, and EOS1. Safety There is no formal safety objective for this study as MIRRAGEN™ and FIBRACOL™ are commercially available, 510K FDA cleared dressings for diabetic foot wounds. Therefore, in accordance with FDA regulations, adverse reactions to the dressings will be recorded and provided to the study Sponsor for required FDA reporting and will be concurrently reported to all Investigators and IRBs. Adverse events associated with application of standard of care dressing will be collected during the course of the study. Collection and reporting of any adverse reaction data, in accordance with FDA regulations and adverse events associated with dressing application will ensure study subject safety.

Surveillance Schedule

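### The interim sample-size recalculation is not limited to pooled data, the final test is unadjusted and three alpha levels are unreconciled, so control of the type I error is not shown

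*Combined protocol and SAP*

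**What the plan says.** All of this is in section 9.2 unless noted.

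- **Interim.** There is one look at about 100 subjects. "The object of the interim analysis is to assess subject outcomes between the groups", in particular harms such as infection, and "to recalculate sample size for the primary endpoint". No formula, power target, lower limit on N, restriction on the data used or stopping boundary is given.
- **Alpha.** "All testing for endpoints will be two-sided". The level is "alpha set at .05 level of significance if no statistical testing is done at the interim analysis". A garbled continuation gives "0.044 if statistical testing is done at N=240", which I read as 0.044 for the final test if a test is done at the interim.
- **Power.** "Group sequential trials with sample sizes of 120 and 120 at the final look achieve 100% power" for 0.70 against 0.35, at a third level, 0.049, with a pooled Z-test.
- **Size.** The synopsis says "For this RCT, N = up to 240 subjects", and section 4.4 gives the same ceiling.
- **Final test.** Chi-square, adjusted by logistic regression. Hochberg is applied across endpoints and does not address the interim.
- **Timing of detail.** A SAP is promised before database lock, which need not be before the interim. The trial is open label (section 4).

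**The concern.** A group-sequential level protects against an extra look when N is fixed in advance. It does not protect against choosing N after seeing the treatment effect and then computing an ordinary chi-square on all the data, because the choice of N can favour the result already in hand.

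The trigger for lowering alpha is a statistical test at the interim. Viewing outcomes by arm or changing N does not trigger it. As written, the sponsor could see closure by arm, reset N, perform no formal test and still use the full 0.05.

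Under the 240 ceiling a recalculation can only keep or reduce N, and a reduction driven by a favourable difference also inflates the error. The primary claim would be open to the criticism that N was chosen to suit the interim result, and the plan holds nothing with which to answer it.

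**Working it through.** **1. The plan's own power figure.** Inputs from section 9.2: n = 120 per arm, p1 = 0.70, p2 = 0.35, two-sided alpha 0.049 (z = 1.969), mean proportion 0.525.

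Power = Φ[(d − z·√(2·p̄(1−p̄)/n)) / √((p1(1−p1)+p2(1−p2))/n)] = Φ[(0.35 − 1.969 × 0.0645)/0.0604] = Φ(3.69) = 0.9999. The stated 100% reproduces, and at 0.05 or 0.044 it is also 99.99%.

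**2. What the plan's effect needs.** For 90% power at alpha 0.05, n = (1.960·√0.49875 + 1.282·√0.4375)²/0.35² = 40.7, so 41 per arm or 82 in all (47 per arm with continuity correction). The 50 per arm at the interim already give 95% power at 0.05 and 94% at 0.044.

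**3. What 240 gives for smaller effects** (control 0.35, alpha 0.05): 65% power for a difference of 0.15, 81% for 0.18, 88% for 0.20 and 91% for 0.21. At alpha 0.044 the figures for 0.18 and 0.21 are 79% and 90%.

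**4. Where the levels come from.** If all 100 subjects have a 12-week outcome (assumption), the information fraction is 100/240 = 0.417 and the correlation of the two Z statistics is √0.417 = 0.645. With N fixed at 240 and a two-sided total of 0.05:

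| Final level | Interim level that makes the total 0.05 |
|---|---|
| 0.049 | 0.0024 (O'Brien-Fleming-type spending) |
| 0.044 | 0.0104 |

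The two reduced levels therefore imply different boundaries, and the plan states neither.

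**5. Type I error if N is reset from the observed difference.** The plan gives no rule, so these are assumptions: 50 per arm at the look, both arms at the same closure rate, observed proportions put into the formula of step 2, N kept within 100 to 240, ordinary pooled Z at the end. The results are from exact binomial enumeration and agree with simulation.

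| Rule | Nominal 0.05, rate 0.35 / 0.525 | Nominal 0.044, either rate |
|---|---|---|
| Fixed N = 240 | 0.050 / 0.046 | 0.045 |
| Reset to 80% power | 0.062 / 0.058 | 0.056–0.057 |
| Reset to 90% power | 0.056 / 0.052 | 0.050–0.051 |

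The ranges at 0.044 depend on whether the sample-size formula uses 0.044 or 0.05.

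**6. Worst case.** For each interim value z₁, take the N in the allowed range that maximises the conditional chance of rejection, Φ[−(c√N − 10z₁)/√(N−100)] + Φ[(−c√N − 10z₁)/√(N−100)], where 10 = √100 and c is the final critical value. Then average over z₁ ~ N(0,1).

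| Allowed final N | 0.05 | 0.049 | 0.044 |
|---|---|---|---|
| 100–240 (may end at the look) | 0.091 | 0.089 | 0.080 |
| 120–240 | 0.071 | 0.070 | 0.063 |
| 190–240 | 0.055 | 0.054 | 0.049 |

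**7. Recalculation from the pooled rate only.** With a target difference of 0.25 and 90% power, the error at nominal 0.05 is 0.051 (rate 0.35) and 0.050 (rate 0.525). With a target of 0.21 it is 0.050 and 0.056. The 0.056 is the discreteness of the chi-square: the same values of N, fixed in advance with no interim, also average 0.056. The pooled rule itself adds nothing material.

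**The case against.** A reader might infer that the recalculation uses the difference between the arms, because the two purposes stand in one sentence. The text does not say so. The between-group purpose is qualified by adverse events, and a recalculation from pooled closure fits the wording just as well. This objection stands: the plan permits effect-based resizing but does not prescribe it.

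A reader might also infer that the final test is simply run at 0.05. That passes over the 0.044 branch and the 0.049 in the power statement. The lower level does help. At 0.044 the 90% rule comes out at about 0.050, and if N can only end between 190 and 240 even the worst case is 0.049. But the plan does not restrict N to that range, and 0.044 is not tied to the recalculation.

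The worst cases need someone to choose N so as to maximise rejection, and the 0.091 also needs the option of ending at 100. They are bounds and should not be read as forecasts. Scenarios with N above 240 are outside the plan as written and would need an amendment.

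Finally, a reader might conclude that 240 never needs revisiting. That holds only near the assumed difference of 0.35. Below about 0.18, power falls under 80%, so checking the assumption is a legitimate wish.

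**Conclusion.** The documents do not support a statement that the type I error is inflated. They support the narrower statement that its control is not shown. The plan couples a between-group look with a change of N, leaves the data and the rule open, ends with an unadjusted test and gives three levels that belong to different situations.

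If the by-arm effect drives N within 100 to 240, the error is about 0.052 to 0.062 at nominal 0.05 and 0.050 to 0.057 at 0.044. The bounds are 0.091 and 0.080, or 0.071 and 0.063 with at least 20 further subjects. If only the pooled rate is used, there is no material inflation from the recalculation.

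These figures rest on assumed rules, 50 evaluable subjects per arm at the look and no covariate adjustment; the bounds also use a normal approximation. The excess under plausible rules is modest, but it bears on the single primary claim. It can be removed only by a rule written before by-arm outcomes are seen, and the current SAP deadline does not guarantee that.

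**What to change.** Amend section 9.2, and the SAP to match, before the interim look. Choose one route for N:

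1. **Fix N at 240** and drop the recalculation. State that this gives 99.99% power for 0.70 against 0.35 and, with control at 0.35, about 80% for a difference of 0.18 and 90% for 0.21.
2. **Keep a recalculation from pooled data.** Use only the two-arm pooled closure proportion, with a written formula, a target difference and power chosen by the sponsor, and 240 as the cap.
3. **If by-arm data are to be used,** write down the rule and the limits on N, and replace the final chi-square by a combination statistic whose stage weights are fixed in advance.

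Under any route, state one interim/final alpha pair. For N fixed at 240 with an efficacy test at the interim, 0.0024/0.049 or 0.0104/0.044 each total 0.05. Keep 0.05 only if no efficacy comparison is made at the interim and N does not depend on the effect. Say who sees by-arm data.

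The cost is a few sentences and the sponsor's freedom to change N after seeing the effect. Route 3 keeps some of that freedom at the price of a less familiar primary test.

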5.1 Subject Completion

- A subject whose index ulcer has closed will be considered as having completed the study
- A subject who completes the Treatment Phase up to TV7 with the wound healed less than 50% will be considered as having completed the study
- A subject who completes the Treatment Phase but still has an unhealed index ulcer will be considered as having completed the study
- A subject who does not complete the Treatment Phase and still has an unhealed index ulcer will be considered as not completing the study

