5.2 Success and Failure

- A subject whose ulcer heals by 13 weeks and has been confirmed as healed two weeks later will be considered a treatment success
- A subject whose ulcer has failed to heal by 50% or greater at TV7 or six weeks after randomization will be considered a treatment failure
- A subject whose ulcer has failed to heal by 13 weeks will be considered a treatment failure
- A subject who is withdrawn from the trial and/or experiences an amputation is also considered a treatment failure

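### The secondary analyses named in section 9.2 give no rule for follow-up that ends by outcome (below 50% at TV7, or healed), and the WOUND-Q fallback test does not test a mean difference

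*Combined protocol and SAP*

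**What the plan says.** Section 9.2 lists the secondary analyses. Time to closure is "time to heal within 6 and 12 weeks using Kaplan-Meier analysis"; no test and no censoring rule are given. Pain is the "change in weekly wound pain VAS score based on GLM repeated measures" (the scale elsewhere is the NPRS), and neuropathy is handled the same way. WOUND-Q is a mean difference in change from baseline to 12 weeks, "using t test if data are normal or Kolmogorov–Smirnov test if data are non-normal".

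Follow-up depends on outcome. Subjects below 50% area reduction at TV7, six weeks after randomization, go to EOS1 and leave (sections 4.2 and 4.5.3.3.3). Weekly visits also stop once the ulcer heals (section 4.3.1).

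The status of these subjects is set in three places:
- Section 5.2: a subject whose ulcer "failed to heal by 50% or greater at TV7 or six weeks after randomization will be considered a treatment failure". The same section adds: "A subject who is withdrawn from the trial and/or experiences an amputation is also considered a treatment failure".
- Section 5.1: a subject who stays "up to TV7 with the wound healed less than 50% will be considered as having completed the study". Healed subjects are also completers there.
- Section 9.2: "Subjects who are withdrawn or lost to follow-up will be included in the ITT analysis" of primary and secondary endpoints, by imputation methods left to the SAP.

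Table 4 in section 9.1 lists "Time to healing within 6 and 12 weeks" and gives the primary endpoint as its supporting data. Section 9.2 says that a formal SAP will be written before database lock, will add detail, and will describe any deviation.

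**The concern.** The only handling rule for incomplete data on secondary endpoints names subjects who are withdrawn or lost. Healed subjects are neither. TV7 exits are completers under section 5.1, and section 5.3 reserves premature discontinuation for non-completers. The footnote to the visit schedule, which brings EOS1 forward for withdrawal, could be read the other way. So the rule does not cover healed subjects and does not clearly cover TV7 exits.

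If the named methods are run in their ordinary form, three things follow:
- **Time to heal.** A TV7 failure is censored at week 6, as if that subject would later heal at the same rate as those who stay. The exit is triggered by poor healing, so the censoring is informative by design. The result would also conflict with section 5.2 and Table 4.
- **Pain and neuropathy.** Classical repeated-measures GLM uses only subjects with every visit. Both healing and TV7 exit remove visits, so the comparison is made in a subset selected by outcome rather than in the randomized groups.
- **WOUND-Q**, a separate matter from the exits. The Kolmogorov-Smirnov test responds to any difference in distribution, not only to a difference in means.

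These p-values enter the Hochberg procedure, which section 9.2 applies to all endpoints, so they can also influence other endpoints' decisions.

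**Working it through.** **The plan's own figure.** Section 9.2 states 100% power for 0.70 versus 0.35 with 120 per arm, two-sided alpha 0.049, pooled Z. The pooled standard error is √(2×0.525×0.475/120) = 0.0645 and the unpooled is √((0.70×0.30+0.35×0.65)/120) = 0.0604. Power = Φ((0.35 − 1.969×0.0645)/0.0604) = 0.9999. This reproduces. No power is stated for the secondary analyses.

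**Inputs.** From the plan: 12-week closure H = 0.70/0.35 and 120 per arm. Assumed, because the documents do not give them: closure by week 6 (h), the share exiting at TV7 (e), and log-rank as the test. Exits are taken as not healed, as section 5.2 classes them. Arms are listed MIRRAGEN/FIBRACOL.

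**(a) Kaplan-Meier with TV7 exits censored at week 6.** KM(12) = 1 − (1−h)×[1 − (H−h)/(1−h−e)].

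With h = 0.35/0.12 and exits 15%/40%: 1 − 0.65×(1 − 0.35/0.50) = 0.805, and 1 − 0.88×(1 − 0.23/0.48) = 0.542.

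| Exits | KM at 12 weeks | Gap in points (true gap 35) |
|---|---|---|
| 8%/20% | 74.9% vs 41.8% | 33 |
| 10%/30% | 76.4% vs 46.9% | 29 |
| 15%/40% | 80.5% vs 54.2% | 26 |
| 20%/20% | 85.6% vs 41.8% | 44 |

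Both curves are too high in every row; the gap can shrink or widen. If exits stay at risk as unhealed to week 12, the curves return to 70% and 35%.

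Log-rank rejection rates, by simulation (20,000 trials, two-sided 0.05, closure times uniform within weeks 1–6 and 7–12):

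| True closure (h) | Exits | Censored at week 6 | Kept at risk |
|---|---|---|---|
| 70/35 (0.35/0.12) | 15/40 | above 99% | above 99% |
| 50/35 (0.20/0.12) | 20/40 | 24% | 67% |
| 50/35 (0.20/0.12) | 15/35 | 26% | 67% |
| 50/35 (0.20/0.12) | 25/25 | 78% | 67% |
| 50/50 (0.20/0.20) | 15/35 | 41% | 5% |
| 50/50 (0.20/0.20) | 20/30 | 14% | 5% |

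In the second row the censored curves read 60.0% versus 54.2%, a gap of 6 points instead of 15. With equal closure and exits 15/35 they read 57% versus 73%, so virtually all false rejections favour the arm with **more** exits. That case also needs stayers in the high-exit arm to heal more often after week 6: 0.30/0.45 = 67%, against 0.30/0.65 = 46%.

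**(b) Complete cases for GLM, closure 70/35.**
- *Weekly reading, no TV7 exits:* 120×0.30 = 36 and 120×0.65 = 78, plus any who close at the last visit. The standard error relative to 120 per arm is √((1/36+1/78)/(2/120)) = 1.56. With exits 15/40, 18 and 30 remain (ratio 2.31).
- *Five-visit reading* (TV1, TV3, TV7, TV9, EOS1; synopsis and section 3): subjects closing after TV9 also have all five values. With uniform closure times that is 4/6 of the closures after week 6. So 120×(0.30 + 0.35×4/6) = 64 and 120×(0.65 + 0.23×4/6) = 96 (ratio 1.25). With exits 15/40, about 46 and 48 remain (ratio 1.59).

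**(c) Kolmogorov-Smirnov with equal means, 120 per arm** (simulated; the distributions are illustrative). Gamma shape 1 versus 2: it rejects in about 50% of trials, against about 5% for Welch's t. Laplace with spread ratio 1.5: about 17%, against 5%.

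**The case against.** Section 9.2 promises a SAP that adds detail and may depart from the protocol, and censoring times are usual SAP content. Section 5.2 and Table 4 already point to the right Kaplan-Meier handling, and section 9.2 promises imputation for secondary endpoints. No passage prescribes week-6 censoring or complete-case deletion; both are what the named methods do by default. Pain and monofilament scores are also recorded at the healing confirmation visit (section 4.5.5). At 70/35, the only effect the plan states, log-rank power barely moves. The large losses need an assumed smaller benefit and assumed exit rates.

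All of this stands as a limit on the size of the point. It does not remove the point, because the methods are already named, their ordinary form conflicts with section 5.2, and the imputation sentence leaves out healed subjects.

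A reader might infer more than the documents support:
- *That the primary endpoint is biased.* It is not: section 5.2 counts TV7 exits as failures. The 6-week closure and time-to-heal analyses are also untouched, since the exit occurs at week 6.
- *That censoring is a route to a false claim for MIRRAGEN.* With equal closure, false rejections favour the arm with more exits. The pilot result in section 1.2 (a doubled rate of area reduction) suggests that this would be the FIBRACOL arm, though it gives no exit rate.
- *That the methods are fixed beyond change.* They are named, and the SAP may still depart from them.
- *That 36 and 78 is the only GLM count.* It holds for the weekly reading; the five-visit time frame loses fewer subjects.

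**Conclusion.** The point holds for the secondary analyses and should be settled before the SAP is final. Week-6 censoring of TV7 failures overstates 12-week closure in both arms and makes the gap depend on exit rates, in a direction that cannot be known in advance: 26 to 44 points against a true 35 in the cases shown. The cost in power is negligible at 70/35. It can be large for a smaller benefit when the control arm has more exits, about 24% against 67%. These sizes rest on assumed exit and week-6 closure rates and on log-rank as the test.

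The GLM loss needs no assumed exit rate. On healing alone the standard error is 1.56 times (weekly) or 1.25 times (five visits, uniform closure times) that of the full sample, and either subset is selected by outcome. It does assume the classical complete-case procedure.

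The Kolmogorov-Smirnov mismatch holds whatever the exits; only its rejection rates depend on the shapes chosen.

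**What to change.** Leave the TV7 exit rule as it is and state the following analysis rules:

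1. **Time to heal, 12 weeks.** Name log-rank as the test. Keep TV7 exits at risk as not healed and censor them at week 12. For withdrawn or lost subjects, reconcile the failure rule in section 5.2 with the imputation sentence in section 9.2, and report the alternative as a sensitivity analysis.
2. **Pain and neuropathy.** Replace repeated-measures GLM by a mixed model on all available visits, with baseline as covariate and contrasts at 6 and 12 weeks. Reconcile the weekly wording with the five-visit time frame. Add an ANCOVA on the EOS1 value as a sensitivity analysis, because the mixed model assumes data missing at random.
3. **WOUND-Q.** Replace the Kolmogorov-Smirnov branch by a test of mean change, such as baseline-adjusted ANCOVA with robust standard errors.
4. **Clarification only.** State that the EOS1 value serves as the 12-week value for percentage area reduction and WOUND-Q, with 100% reduction for confirmed healed wounds.

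The cost is wording and some programming. No new visits or data are needed, because EOS1 already records wound size, pain, monofilament and WOUND-Q (sections 4.5.4 and 8.8).
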